7.2 Method of Treatment Assignment

At the time of the screening visit, immediately after informed consent is obtained and before any study-related procedures are performed, the investigative site will access the interactive response technology (IRT) for assignment of the subject identification number. This number will be unique across all sites. All enrolled subjects, including those not randomized or dosed, will be assigned sequential subject numbers. The subject number may not be used for any other subject. If a potential subject is rescreened, they will be given a new identification number.

Eligible subjects will be centrally randomized using IRT to receive oral treatment during the Induction Period with BMS-986165 at 6 mg BID or 3 mg BID or placebo BID, according to a computer-generated block randomization scheme and in accordance with stratification criteria. Randomization numbers will be assigned prior to dosing ([Section 5.1](#)).

Before the study is initiated, each user (at investigative sites) will receive log-in information and directions on how to access the IRT. Study treatment will be dispensed at study visits as shown in [Section 2](#) (Schedule of Activities).

7.3 Blinding

7.3.1 Maintaining the Blind

Blinded treatment assignments will be managed using IRT.

All capsules (BMS-986165 3 mg and placebo) have an identical matching placebo capsule in order to maintain the blind. [REDACTED] Investigative site staff, Sponsor and designee personnel, and subjects and their families will remain blinded to treatment assignments.

The Sponsor may perform an unblinded interim analysis of study data prior to final data analysis. A SAP, which will include a section on interim analysis, will be created to fully detail the activities around the interim analysis.

The DMC may review unblinded data summaries and listings, at their request (see [Section 5.1.5](#)). DMC processes and procedures will be outlined in the DMC Charter.

Designated staff of Bristol-Myers Squibb Company may be unblinded (obtain the randomization codes) prior to database lock to facilitate the bioanalytical analysis of [REDACTED] and immunogenicity. A bioanalytical scientist in the Bioanalytical Sciences department of Bristol-Myers Squibb Research & Development (or a designee in the external central bioanalytical laboratory) will be unblinded to (may obtain) the randomized treatment assignments in order to minimize bioanalytical analysis of samples.

7.3.2 Circumstances for Unblinding

Blinding of treatment assignment is critical to the integrity of this clinical study. However, in the event of a medical emergency or pregnancy in an individual subject in which knowledge of the IP is critical to the subject's management, the blind for that subject may be broken by the investigator. The subject's safety takes priority over any other considerations in determining if a treatment assignment should be unblinded.

Before breaking the blind of an individual subject's treatment, the investigator should determine that the unblinded information is necessary (ie, determine if it will alter the subject's immediate management). In many cases, particularly when the emergency is clearly not related to the IP, the problem may be properly managed by assuming that the subject is receiving active product. It is highly desirable that the decision to unblind treatment assignment be discussed with the medical monitor, but the investigator always has ultimate authority for the decision to unblind. The principal investigator should only call in for emergency unblinding AFTER the decision to discontinue the subject has been made.

In case of an emergency, the investigator has unrestricted access to randomization information via IRT and is capable of breaking the blind through the IRT system without prior approval from the Sponsor. After the unblinding, the investigator shall notify the medical monitor in order to discuss subject safety and whether the subject should remain in the study. The method of unblinding for emergency purposes is described in the IRT manual. Subject and unblinded treatment information and the reason for the blind being broken, must be recorded on the appropriate study status page of the electronic case report form (eCRF).

In cases of accidental unblinding, contact the medical monitor and ensure every attempt is made to preserve the blind. Any request to unblind a subject for nonemergency purposes must be discussed with the medical monitor.

7.3.3 Unblinding for Week 12 Analysis

An unblinded analysis of data through Week 12 will be performed after all subjects complete their Week 12 efficacy assessments or have discontinued prior to Week 12. A select group of BMS personnel who are not involved in the conduct of the study will review the unblinded results to write a clinical study report. Following the Week 12 analysis until the end of the study, the investigators, subjects, and clinical study team members who directly cooperate with the site staff will continue to remain blinded to the initial treatment assignment. Details of maintaining the blind

following the unblinded analysis will be finalized in the SAP prior to the Week 12 database lock. A final analysis will be performed after all subjects complete the Week 104 visit or discontinue prior to the Week 104 visit, and a clinical study report will be written.

7.4 Dosage Modification and/or Interruption

There is no provision for dose modification of study treatment. [REDACTED]. Modification of other background CD therapies or dose regimens is not permitted during study participation. [REDACTED]

[REDACTED] If a subject's clinical condition worsens (eg, flares) during the Induction Period to the extent that rescue therapy is required based on the investigator's judgment, the subject must discontinue study treatment (IP or placebo) for appropriate alternative available treatment.

If treatment is interrupted for a subject due to an AE, study treatment can be restarted in consultation with the medical monitor.

7.5 Preparation/Handling/Storage/Accountability

The IP should be stored in a secure area according to local regulations. It is the responsibility of the investigator to ensure that IP is only dispensed to study subjects. The IP must be dispensed only from official study sites by authorized personnel according to local regulations.

The product storage manager should ensure that the study treatment is stored in accordance with the environmental conditions (temperature, light, and humidity) as determined by BMS. If concerns regarding the quality or appearance of the study treatment arise, the study treatment should not be dispensed and BMS should be contacted immediately.

Study treatment not supplied by BMS will be stored in accordance with the package insert.

IP documentation (whether supplied by BMS or not) must be maintained that includes all processes required to ensure drug is properly stored and administered. This includes documentation of drug storage, administration and, as applicable, storage temperatures, reconstitution, and use of required processes (eg, required diluents, administration sets).

Guidance and information for the final disposition of unused study treatments are provided in [APPENDIX 2](#) and the Study Reference Manual.

7.6 Treatment Compliance

Study treatment compliance will be periodically monitored using standard drug accountability procedures (comparing the number of capsules returned to number dispensed, considering the expected regimen and any reported missed doses). Drug accountability will be reviewed by the investigative site staff at each visit to confirm treatment compliance. Site staff will discuss any discrepancies with the subject and remind the subject of the importance of compliance with the assigned regimen. A real-time monitoring platform may be used.

[figure not shown]
7.7 Concomitant Therapy

All medications taken from within 4 weeks before the first dose of study treatment until 30 days after the last dose of IP or last visit (whichever comes later) of study treatment must be recorded on the eCRF.

Other than existing treatment for CD (with restrictions as described in the eligibility criteria [Section 6]), concomitant medications (prescription, over-the-counter [OTC], or herbal) should be administered during the study only if they are prescribed for treatment of specific clinical events.

7.7.1 Prohibited and/or Restricted Treatments

Restrictions and prohibitions on prior and concomitant medications are as follows:

- 1) Prior exposure to BMS-986165 is prohibited.
- 2) 
- 3) Nonsteroidal anti-inflammatory drugs (NSAIDs) may be used on an as-needed basis during the study for indications other than CD-related pain (eg, headache), but use is not recommended. Assessment of AP is a component of the CDAI and PRO2 instruments, and NSAIDs are likely to confound the assessment of efficacy in this study, ie, by improving or exacerbating AP related to CD.
- 4) Prior treatment with specific lymphocyte-depleting agents, such as alemtuzumab, rituximab, are prohibited within 12 months prior to the first dose of study treatment during the Induction Period.
- 5) Not applicable per Global Revised Protocol v5.0
- 6) Receipt of either lymphocyte apheresis or selective monocyte, granulocyte apheresis (eg, Cellsorba™) is prohibited.
- 7) Required washout periods for individual immunomodulatory and biologic drugs are provided in [APPENDIX 7](#).
- 8) Live vaccines are prohibited 90 days prior to randomization, during the Induction Period or Maintenance Period, or within the 2 months after the last dose. Heat-killed, or otherwise inactivated, protein or subunit vaccines such as influenza and pneumococcal vaccines, nucleic acid vaccines that do not encode potentially infectious virus, and replication-incompetent recombinant vector vaccines may be received at any time on study. The effectiveness of vaccination in subjects receiving BMS-986165 has not been studied. Similarly, the effectiveness of vaccination in subjects who will shortly receive BMS-986165 (eg, subjects in the screening period) has not been studied.
- 9) For COVID-19 vaccine information, refer to [APPENDIX 19](#).

10) Exposure to any investigational drug within 4 weeks or 5 half-lives (whichever is longer) before the first dose of study treatment is prohibited (Exclusion Criterion 1)r); [Section 6.2](#)).

7.7.2 Existing Therapies for Crohn's Disease

Use of concomitant 5-ASAs, probiotics, antibiotics to treat luminal CD, and corticosteroids (prednisone \leq 20 mg/day or equivalent, or ileal-release budesonide \leq 9 mg/day [eg, Entocort[®] EC]) is permitted. All subjects will continue their existing CD treatment(s) during the study as follows (if the treatment complies with the eligibility criteria; [Section 6](#)), unless dose modification or discontinuation is required for subject safety reasons:

- 5-ASAs must be at stable doses for at least 2 weeks prior to the first dose of study treatment on Day 1 of the Induction Period and must be maintained at stable doses during the Induction Period.
- CD-related antibiotics (eg, ciprofloxacin, metronidazole, etc.) must be at stable doses for at least 2 weeks prior to the first dose of study treatment on Day 1 of the Induction Period and must be maintained at stable doses during the Induction Period.

If subjects were previously prescribed any of the above medications, they must have been discontinued for \geq 4 weeks prior to the randomization visit.

- Probiotics must be at stable doses for at least 2 weeks prior to the first dose of study treatment on Day 1 of the Induction Period and must be maintained at stable doses during the Induction Period. During the Maintenance Period, a dose decrease is permitted if due to probiotics-related toxicity.
- Corticosteroids
 - Prednisone \leq 20 mg QD PO (or equivalent) or ileal-release budesonide \leq 9 mg QD PO (eg, Entocort[®] EC) must be stable for at least 2 weeks prior to randomization, with dose stabilization during the Induction Period. [REDACTED]
 - Use of IV corticosteroid is prohibited within 14 days prior to or during the Screening Period and throughout the duration of the Induction Period and Maintenance Period.

Immunomodulators and biologics must be discontinued prior to the first dose of study treatment as outlined below and are prohibited during the study:

- Prior exposure to the immunomodulators 6-MP, AZA, and MTX is permitted, but these agents must be discontinued for at least 4 weeks prior to the first dose of study treatment on Day 1 of the Induction Period. Treatment with cyclosporine, mycophenolate mofetil, leflunomide, tacrolimus, or JAK inhibitors must be discontinued prior to the first dose of study treatment on Day 1 of the Induction Period as described in [APPENDIX 7](#).
- The washout period for biologics is discussed in [Section 5.1.1](#) and [APPENDIX 7](#). The washout period for infliximab, adalimumab or certolizumab pegol may be waived for subjects with an undetectable drug level on a TDM assay performed in routine clinical practice, or in screening.

The washout period for subjects who have received vedolizumab maintenance therapy for > 14 weeks or ustekinumab therapy for > 12 weeks may similarly be waived, if a TDM assay shows undetectable drug levels.

7.8 Treatment After the End of the Study

[figure not shown]
BMS reserves the right to terminate access to BMS-supplied study treatment if any of the following occur: a) the study is terminated due to safety concerns or other reasons, including but not limited to, lack of efficacy and/or failure to meet study objectives; b) development of BMS-986165 for the treatment of CD and/or the development of the compound is terminated for other reasons, including but not limited to lack of efficacy and/or failure to meet study objectives; c) the subject can obtain medication from a government sponsored or private health program. In all cases, BMS will follow local regulations.

8 DISCONTINUATION CRITERIA

8.1 Discontinuation from Study Treatment

Subjects MUST discontinue IP (and non-IP at the discretion of the investigator) for any of the following reasons:

- Subject requests to stop study treatment. Subjects who request to discontinue study treatment will remain in the study and must continue to be followed for protocol-specified follow-up procedures. The only exception to this is when a subject specifically withdraws consent for any further contact with him/her or persons previously authorized by subject to provide this information.
- Subject meets the following criteria for laboratory abnormalities in 2 sequential laboratory measurements taken 3 to 5 days apart (2 additional days are permitted to allow for local logistics):
 - Absolute neutrophil count $< 0.75 \times 10^9/L$ ($< 750/mm^3$)
 - Absolute lymphocyte count $< 0.5 \times 10^9/L$ ($< 500/mm^3$)
 - Hemoglobin < 8.0 g/dL or a decrease of $> 30\%$ from baseline
 - Platelet count $< 75 \times 10^9/L$ ($< 75,000/mm^3$)
 - An increase in serum creatinine $> 50\%$ over the average of screening and baseline values AND an absolute increase in serum creatinine > 0.5 mg/dL ($> 44.2 \mu\text{mol/L}$)
 - Creatine kinase (CK) elevations > 10 times the ULN, unless the causality is known not to be medically serious (eg, exercise-induced)

- Subjects who develop a significant infection during the study, defined as any infection (viral, bacterial, or fungal) requiring parenteral antimicrobial therapy, or meeting the SAE criteria
- Termination of the study by BMS or a specific dose arm (for subjects receiving that dose) by BMS. Subjects enrolled prior to Protocol v3.0 and who may have been randomized to blinded BMS-986165 12 mg QD treatment do not need to be discontinued.
- Loss of ability to freely provide consent through imprisonment or involuntary incarceration for treatment of either a psychiatric or physical (eg, infectious disease) illness
- Unblinding of a subject's treatment assignment for any reason (emergency or nonemergency)
- Inability or failure to comply with protocol requirements
- Pregnancy
- 
- Subject meets any of the following criteria for liver-related laboratory abnormalities. If these abnormalities are identified, repeat testing should occur within 48 to 72 hours and these results should be discussed with the BMS medical monitor/designee. Additional recommendations on the recognition and investigation of potential drug-induced liver injury (DILI) are given in [Section 9.3.8](#).
 - ALT or AST > 8× ULN on a single occasion
 - ALT or AST > 5× ULN for more than 2 weeks
 - ALT or AST > 3× ULN and total bilirubin > 2× ULN or international normalized ratio (INR) > 1.5
- ALT or AST > 3× ULN with the appearance of fatigue, nausea, vomiting, right upper quadrant pain or tenderness, fever, rash, and/or eosinophilia (> 5%)
- Any other serious or severe AE or intercurrent illness, that, in the opinion of the investigator and after consultation with the medical monitor or designee, indicates that continued participation in the study is not in the best interest of the subject. If study treatment is discontinued due to an AE, the AE eCRF must be completed to show that the AE caused discontinuation

Refer to the Schedule of Activities ([Section 2](#)) for data to be collected at the time of treatment discontinuation and follow-up and for any further evaluations that can be completed.

In the case of pregnancy, the investigator must immediately notify the BMS medical monitor or designee of this event. In the event a female subject becomes pregnant during a clinical trial, the study treatment must be discontinued immediately. In most cases, the study treatment will be permanently discontinued in an appropriate manner (eg, dose tapering if necessary for subject safety). Please call the BMS medical monitor within 24 hours of awareness of the pregnancy.

All subjects who discontinue BMS-986165 should comply with protocol-specified follow-up procedures as outlined in [Section 2](#). The only exception to this requirement is when a subject withdraws consent for all study procedures including posttreatment study follow-up or loses the ability to consent freely (ie, is imprisoned or involuntarily incarcerated for the treatment of either a psychiatric or physical illness). Replacement of subjects is not permitted.

If study treatment is discontinued prior to the subject's completion of the study, the reason for the discontinuation must be documented in the subject's medical records and entered on the appropriate eCRF page.

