The reproductive toxicology studies for BMS-986165 are complete and detailed in the IB. Briefly, BMS-986165 is not genotoxic. BMS-986165 was neither teratogenic nor fetotoxic up to the highest evaluated dose of 50 mg/kg/day, and there was no evidence of teratogenicity or effects on development in reproductive and developmental toxicity studies in rats and/or rabbits. These findings support the contraception requirements for this study.

In addition, a completed thorough QT_c study has excluded a clinically meaningful effect on QT interval at doses of up to 36 mg (a supratherapeutic dose).

Taken together, these data suggest that BMS-986165 may be beneficial, safe and well tolerated in patients with active CD. In addition, there is no evidence for clinically significant DDIs at the concentrations expected in this study, or clinically meaningful effects on electrocardiogram (ECG) parameters. The reproductive risk potential has not been comprehensively evaluated in humans.

BMS-986165 is an immunomodulatory IP and a potential immunosuppressant. [REDACTED]

[REDACTED]

The global coronavirus disease 2019 (COVID-19) pandemic has been identified as a potential risk to clinical study subjects in general, and it may particularly affect individuals with underlying chronic diseases. The risk of severe acute respiratory syndrome coronavirus 2 (SARS-CoV-2) infection in subjects taking BMS-986165 is unknown. The individual benefit-risk considerations regarding COVID-19 infection remains the responsibility of the investigator. In order to reduce the risk of asymptomatic SARS-CoV-2 at baseline, subjects will be tested for SARS-CoV-2 during the screening period, as close as possible prior to randomization (refer to [Section 9.10](#)). Testing for SARS-CoV-2 to inform decisions on subject care during the study, should follow local standard of care and clinical practice. Potential subjects with recent COVID-19 infection will be excluded until their symptoms have completely resolved for 30 days prior to receiving first dose of IP. The protocol provides guidance to investigators on temporary discontinuation of IP in the case of suspected or proven COVID-19 infection. The protocol also provides guidance on restarting IP following recovery from a COVID-19 infection, which must be confirmed by a negative diagnostic test for SARS-CoV-2 ([Section 8.2.1](#)).

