8.1.1 Post Study Treatment Study Follow-up

Subjects who discontinue study treatment will continue to be followed for 28 days post last dose of study medication.

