8.2.1 Temporary IP Discontinuation

The following criteria for temporary interruption of study treatment apply:

- For those subjects who present with signs and/or symptoms of COVID-19 during the study, the study treatment should be temporarily interrupted while the subject undergoes diagnostic testing for SARS-CoV-2 (see [Section 9.10](#)).
- Study treatment must be temporarily interrupted for subjects who test positive for SARS-CoV-2 until complete recovery (if symptomatic), and a negative molecular test result is obtained. Study treatment may be restarted at investigator discretion following consultation with the BMS medical monitor/designee provided that the subject meets the criteria outlined in [Section 9.10](#).

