9.3.2 Time Period and Frequency for Collecting AE and SAE Information

The collection of nonserious AE information should begin at initiation of study treatment until the follow-up visit at Week 108 or the last visit, at the time points specified in the Schedule of Activities ([Section 2](#)). Nonserious AE information should also be collected from the start of the treatment period at Day 1.

The Reference Safety Information in [Appendix 1](#) of the IB should be used to determine expectedness of SAEs for expedited reporting.

All SAEs must be collected from the time of signing the consent, including those thought to be associated with protocol-specified procedures, and within 30 days of discontinuation of dosing.

All AEs and SAEs related to SARS-CoV-2 infection must be collected from the time of signing the consent to the end of the safety follow-up period (30 days after treatment discontinuation) [REDACTED]

The investigator must report any SAE that occurs after this time period and that is believed to be related to study treatment or protocol-specified procedure.

- Medical occurrences that begin before the start of study treatment but after obtaining informed consent will be recorded on the appropriate section of the eCRF module.
- All SAEs will be recorded and reported immediately to Sponsor or designee but no later than 24 hours after awareness of the event, as indicated in [APPENDIX 3](#).
- The investigator will submit any updated SAE data to the Sponsor or designee immediately but no later than 24 hours of updated information being available.

Investigators are not obligated to actively seek AEs or SAEs in former study subjects. However, if the investigator learns of any SAE, including a death, at any time after a subject has been discharged from the study, and he/she considers the event reasonably related to the study treatment or study participation, the investigator must promptly notify the Sponsor or designee.

The method of evaluating and assessing causality of AEs and SAEs and the procedures for completing and reporting/transmitting SAE reports are provided in [APPENDIX 3](#).

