9.10 SARS-CoV-2 Testing

Diagnostic testing for SARS-CoV-2 infection refers to a molecular test (PCR) or antigen test for SARS-CoV-2 infection, performed according to local standard of care. PCR testing is preferred. Antibody testing is not acceptable as a diagnostic test for SARS-CoV-2 infection.

Diagnostic testing for SARS-CoV-2 infection should be performed as close as possible to randomization and must be confirmed as “negative” prior to randomization.

Subjects will be screened for AEs (including signs and symptoms of COVID-19) at each study visit. Subjects will be instructed to contact the investigator at any time if they develop an intercurrent illness, including a diagnosis, or signs and symptoms of COVID-19, which will enable close monitoring and additional screening for the infection between study visits.

The investigator should obtain a diagnostic test for SARS-CoV-2 infection if COVID-19 is clinically suspected. If a subject report having recent direct contact with someone known to have COVID-19, the subject should undergo diagnostic testing for SARS-CoV-2.

IP should be temporarily interrupted in subjects who present with signs and/or symptoms suggestive of COVID-19 while the subject undergoes diagnostic testing for SARS-CoV-2 infection. This testing should be performed as soon as feasible.

IP must be temporarily interrupted in subjects who test positive for SARS-CoV-2 infection. Such subjects should continue to be followed by the investigator. Such subjects must meet all the criteria outlined below prior to restarting IP. The final decision to restart IP must be made in consultation with the BMS medical monitor/designee.

Subjects with a positive diagnostic test for SARS-CoV-2 infection during the screening period may be considered eligible for the study once they meet all eligibility criteria related to active infection, and after meeting the criteria outlined below.

Criteria to rescreen or recommence IP after a positive SARS-CoV-2 test:

- Negative follow-up molecular test for COVID-19 based on institutional, local, or regional guidelines, and
- At least 10 days (20 days for severe/critical illness) have passed since symptoms first appeared or positive test result, and
- At least 24 hours have passed since last fever without the use of fever-reducing medications, and
- Symptoms (eg, cough, shortness of breath) have resolved, and

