
• Medical or surgical procedure (eg, endoscopy, appendectomy): the condition that leads to the procedure is the AE.• Situations in which an untoward medical occurrence did not occur (social and/or convenience admission to a hospital).

DEFINITION OF SAE

If an event is not an AE per definition above, then it cannot be an SAE even if serious conditions are met.

SERIOUS ADVERSE EVENTS

A serious adverse event (SAE) is defined as any untoward medical occurrence that, at any dose:

Results in death

Is life-threatening (defined as an event in which the subject was at risk of death at the time of the event; it does not refer to an event which hypothetically might have caused death if it were more severe)

Requires inpatient hospitalization or causes prolongation of existing hospitalization (see NOTE below)
 
NOTE:
 
The following hospitalizations are not considered SAEs in BMS clinical studies:
 
 • A visit to the emergency room or other hospital department < 24 hours, that does not result in admission (unless considered an important medical or life-threatening event) • Elective surgery, planned prior to signing consent • Admissions as per protocol for a planned medical/surgical procedure • Routine health assessment requiring admission for baseline/trending of health status (eg, routine colonoscopy) • Medical/surgical admission other than to remedy ill health and planned prior to entry into the study. Appropriate documentation is required in these cases • Admission encountered for another life circumstance that carries no bearing on health status and requires no medical/surgical intervention (eg, lack of housing, economic inadequacy, caregiver respite, family circumstances, administrative reason) • Admission for administration of anticancer therapy in the absence of any other SAEs (applies to oncology protocols)

Results in persistent or significant disability or permanent damage

Is a congenital anomaly/birth defect

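### Section 8.1 requires study drug to stop for a serious SARS-CoV-2 infection, Sections 8.2.1 and 9.10 allow interruption and restart, and no legible text says which rule prevails

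*Combined protocol and SAP*

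**What the plan says.** Section 8.1 opens its list with "Subjects MUST discontinue IP (and non-IP at the discretion of the investigator) for any of the following reasons". One item is a significant infection, defined as "any infection (viral, bacterial, or fungal) requiring parenteral antimicrobial therapy, or meeting the SAE criteria". Viral infections are named, and the legible item has no carve-out for SARS-CoV-2. Section 8.1.1 then provides that "Subjects who discontinue study treatment will continue to be followed for 28 days post last dose of study medication"; neither section describes a way back onto drug.

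Section 8.2.1 starts from a positive test: "Study treatment must be temporarily interrupted for subjects who test positive for SARS-CoV-2 until complete recovery (if symptomatic"), and until a negative molecular result is obtained. It lets the investigator restart treatment after consulting the medical monitor, provided the Section 9.10 conditions are met. Section 9.10 repeats the temporary interruption and gives one list of conditions for both rescreening and restarting. One condition is "At least 10 days (20 days for severe/critical illness) have passed since symptoms first appeared or positive test result". Neither section confines its rule to non-serious infections.

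Two other places bear on the overlap. The SAE definition in Appendix 3 includes an event that "Requires inpatient hospitalization or causes prolongation of existing hospitalization". Section 9.3.2 foresees serious SARS-CoV-2 events: "All AEs and SAEs related to SARS-CoV-2 infection must be collected from the time of signing the consent".

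**The concern.** The same clinical event can meet both triggers. One rule requires study drug to be discontinued. The other requires it to be held and allows it to be given again. A site that follows Section 9.10 to the letter could re-expose a subject whom Section 8.1 says must stop.

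The main stake is safety. This is a mandatory stop for serious infection, on a drug that Section 3.2.3 describes as a potential immunosuppressant. Whether a subject goes back on drug should not turn on which section a site consulted. A lesser stake is uniform conduct, because treatment status before Week 12 feeds the imputation rule in Section 10.4.2.

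**Working it through.** The plan gives no figure to reproduce, so the check is mainly a comparison of texts.

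| | Section 8.1 | Sections 8.2.1 and 9.10 |
|---|---|---|
| Trigger | Infection (viral included) that needs parenteral antimicrobials or meets SAE criteria | Positive SARS-CoV-2 test, no limit by seriousness |
| Action | Mandatory discontinuation | Mandatory temporary interruption |
| Restart | None described; 28-day follow-up in 8.1.1 | Permitted, at discretion, with the medical monitor |
| Reference to the other rule | None legible | None legible |

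**Step 1: is there an overlap?** Take a subject on study drug, with a positive test, admitted as an inpatient because of COVID-19. Admission makes the event an SAE (Appendix 3), so 8.1 applies. The positive test brings in 8.2.1 and 9.10. The overlap is not empty. Severe and serious are different terms in Appendix 3, so not every severe case is an SAE, but hospitalised or life-threatening cases are.

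**Step 2: does other text settle it?** Section 7.4 allows restart after an interruption for an AE, in consultation with the medical monitor, but does not mention the 8.1 list. Other items in 8.1 state their exceptions: creatine kinase rises with a benign cause, and subjects already on 12 mg QD. The infection item states none.

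**Step 3: how many subjects?** The documents give no rate. As an assumption only, let 5% to 20% of about 240 subjects have COVID-19 on study, and 2% to 10% of those cases meet SAE criteria:
- low: 240 × 0.05 × 0.02 = 0.24
- high: 240 × 0.20 × 0.10 = 4.8

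If cases fall evenly over a mean exposure of 52 to 104 weeks (also assumed), the 12-week Induction share is:
- low: 0.24 × 12/104 = 0.03
- high: 4.8 × 12/52 = 1.1

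**Step 4: can it reach Week 12?** A subject who stops at Week 6 is followed for 28 days, to Week 10. If no Week 12 assessment exists, Section 10.4.2 imputes non-response. A subject who restarts can have an observed Week 12 result. The status changes only if that observed result is a response and no other imputation trigger, such as prohibited medication, applies. With at most about one such subject expected across all arms, the largest single-subject shift is 1/60 = 1.7 percentage points for placebo or 1/90 = 1.1 for an active arm.

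**The case against.** The strongest reply is that the rules can be read together. Section 8.1 says discontinue, whereas other sections add the word permanently when they mean it. Even for pregnancy, another 8.1 trigger, the text makes discontinuation permanent in most cases rather than all. Section 8.2.1 is headed as temporary discontinuation and is the specific COVID-19 rule. This reading is plausible, but no legible text adopts it. An item in a mandatory list, followed only by 28 days of follow-up, reads more naturally as final.

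The second reply is that conduct is controlled. Restart is optional and needs medical monitor consultation, and SAEs reach the sponsor within 24 hours. A site that interrupts drug and then stops it breaches neither section. This stands and narrows the point: sites could diverge, and a reader who infers that they necessarily would goes beyond the documents. It does not tell the site or the monitor which rule to apply.

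Third, the 20-day clause has a use in rescreening, where no study drug has been given and 8.1 does not apply. That is correct, so the clause alone does not prove that restart after a serious case was intended. The list does also govern restarting, without excluding such cases.

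Fourth, text is redacted in 8.1, 7.4 and 9.3.2, and an exception may lie there. This cannot be ruled out and lowers confidence.

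**Conclusion.** The conflict stands on the legible text: a SARS-CoV-2 infection that meets SAE criteria or needs parenteral antimicrobials falls under two rules that differ on restart, with no order of precedence. It should be fixed because it concerns a mandatory safety stop and costs little. Confidence is moderate, given the redactions and the unstated but possible harmonising reading. The number affected is likely to be small; the range of about 0.2 to 5 subjects rests wholly on assumed rates.

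Two further inferences are tempting and are not supported:

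- **That the conflict materially changes the primary outcome.** Imputation for discontinuation applies only where Week 12 assessments are absent, so the plan foresees some being obtained after stopping. Section 5.1.2 also requires an early-termination endoscopy between Weeks 4 and 12. The expected number in Induction is about one subject at most under the upper assumptions. Any effect is incidental.
- **That the passages contradict each other on the test needed to restart.** Section 3.2.3 says recovery "which must be confirmed by a negative diagnostic test for SARS-CoV-2", and Section 9.10 counts antigen tests as diagnostic. But 3.2.3 is a summary that points to 8.2.1 and authorises no restart. Both operative sections require a molecular test, which is one kind of diagnostic test. The summary is less specific, not contradictory.

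**What to change.** Reconcile Sections 8.1, 8.2.1 and 9.10. State in both 8.1 and 9.10 which rule governs a SARS-CoV-2 infection that meets SAE criteria or needs parenteral antimicrobial therapy, and cross-refer the two. Depending on the decision, this means either an explicit exception in the 8.1 infection item, or wording in 8.2.1 and 9.10 that limits restart to cases outside 8.1. The sponsor's clinical and safety team decides which rule stands; this review takes no position. If a redacted passage already holds the exception, a cross-reference to it is enough.

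Naming the molecular test in Section 3.2.3 would be a tidy editorial change, but it is optional.

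The cost is a few sentences in the next amendment. No procedure, visit, subject or analysis is added.
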